#### **APPROACH:**

**Preliminary studies:** The Vanderbilt Epicenter investigators have experience in the conduct of operational quasi-experimental studies. Specifically, we recently conducted a successful pragmatic cluster randomized, crossover study of 9,340 patients admitted to 5 adult ICUs from July 2012 through July 2013 to assess if daily chlorhexidine (CHG) bathing reduced HAIs. The

[figure not shown]
primary prespecified outcome was a composite of central line-associated bloodstream infections (CLABSIs), catheter-associated urinary tract infections (CAUTIs), ventilator-associated pneumonia (VAP), and *C. difficile* infections. After adjusting for age, sex, race/ethnicity, unit of admission, time, comorbid conditions, and admission white blood cell count, no significant difference between groups in the rate of the primary outcome was detected. This study demonstrates Vanderbilt's capacity to support large-scale trials evaluating infection prevention interventions.

#### **RESEARCH DESIGN AND METHODS:**

**Study design:** Pre-post withdrawal quasi-experimental study using interrupted time series analysis.

**Study sites:** Six inpatient medical units within Vanderbilt University Hospital will serve as study units. These have been selected due to a higher rate of HO-MDRO/*C. difficile* incidence and/or a higher proportion of admissions comprising LCTF patients. The proposed acute care units have an average of 4,952 patient days per month with LTCF residents comprising 4.3-5.6% of unit admissions. This percentage is likely an underestimation because not all places of patient origin are documented and transfers between units within VUH are not included in this analysis. The HO-MDRO/*C. difficile* rate of these 6 units combined was 4.62 per 1,000 patient days for 2014.

**Study procedures:** After a 6 month baseline period, all units will be transitioned to a 6 month intervention period where all patients transferred onto the study units with LTCF origin prior to admission will be placed on preemptive Contact Precautions (Figure 5). Both patients admitted directly to a study unit as well as patients transferred from a non-study unit onto a study unit will be included under the policy. A washout period of 2 weeks will be introduced before a post-intervention withdrawal period of 6 months is implemented.

Inclusion/exclusion criteria: All patients admitted to the unit will be included in the study. There will be no exclusion criteria.

**Primary outcome - Rate of hospital-onset MDRO and** *C. difficile* **infections:** Aggregate rates of all hospital-onset (HO)-MDRO infections (Table 3), including MRSA, *C. difficile*, VRE, ESBL+ GNB, CRE, and MDR *Acinetobacter*, on participating units will be calculated. As active surveillance for these pathogens is not performed at VUH, only culture specimens obtained for clinical decision making will be included. Specimens from any site (e.g. blood, urine, wound) will be included. These events will be captured daily using the Vanderbilt Infection Prevention Electronic Resource (VIPER), an HAI surveillance platform that monitors laboratory results in real time. Events will be classified as HO if the specimen was collected >3 days after admission to VUH (i.e. on or after day 4).

Secondary outcomes:

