ESBL + GNB (extended-spectrum beta-lactamase producing gram- negative bacillus)	Any E. coli , K. pneumoniae and K. oxytoca demonstrated to have ESBL activity based on results from BD Phoenix through microdilution methodology. The BD Phoenix performs ESBL testing using cephalosporins (ceftazidime/cefotaxime/ceftriaxone) + clavulanic acid.

Table 3:	Definitions	of MDROs	Included in	Primar	y Study	y Outcome
----------	-------------	----------	-------------	--------	---------	-----------

2) Subgroup examinations of individual pathogen HO-infection rates for the overall study population and the aggregate HO-MDRO/*C. difficile* infection rate for each individual study unit

**Covariates:** Several factors may affect the impact of the intervention on the primary outcome. These will be measured and included in the analysis.

**1) Hand hygiene compliance:** Study unit compliance with hand hygiene as monitored by the Vanderbilt Hand Hygiene Program^34 will be included for analysis.

2) PPE compliance: Trained study personnel will perform audits of PPE use by HCP caring for patients placed into the preemptive intervention.

**3) Antimicrobial utilization:** Use of broad-spectrum antibiotics is currently tracked as a part of the VUMC Antibiotic Stewardship Program (Co-directed by Epicenter investigator [name]). Because antibiotic use is a factor in the acquisition of MDROs and *C. difficile*, we will include a measure of broad-spectrum antimicrobial use in the analysis (measured as days of therapy [DOT]).

**Analysis:** The rates of the primary and secondary outcomes will be compared for the following phases, defined *a priori*: 6 month baseline period, 6 month intervention period, and 6 month withdrawal period. In addition, a more robust interrupted time-series regression analysis with Newey-West standard errors will be performed using bimonthly outcome rates (which will provide 12 separate time point measurements for each period).

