**Sample size considerations:** Existing data were used to assess sample size adequacy. Using patient-days, the mean patient days per period will be 4,952 patient days/month for a total of 29,710/period. The rate of HO-MDROs on the units of interest is 4.6/1000 patient days for an average of 137 evaluable events per period. This study will have 80% power to detect a true difference in infection rates of 1.4/1000 patient days. That means a reduction by approximately 42 events in the intervention period. Nursing home admissions (those that will receive the intervention) are at least 4.3-5.6% on target units which is likely an underestimate given the current reporting system.

**Safety:** A data safety monitoring board (DSMB) will be created to oversee any potential adverse events that would require further assessment and intervention. At present 100% of falls, including all falls with harm, have an event review as part of the VUH quality program. The current fall rate on the four proposed units is 2.6 falls/month. The DSMB will review the event analysis of all falls on the unit on a quarterly basis with more in depth interim analysis of all falls stratified by study intervention. Due to the low rates of baseline falls, there is the potential for low case counts to cause large percentage increases, making a pre-defined threshold difficult for stopping the trial. If a sustained, significant increase in falls is seen and thought to be due to the Contact Precautions intervention, then the study will be halted.

**Limitations and future directions:** The evaluation of preemptive Contact Precautions for patients with LTCF exposure will be conducted in an academic, tertiary referral hospital with high rates of hand hygiene compliance. Preemptive isolation is a supplementary strategy and may not be generalizable to acute care hospitals with suboptimal hand hygiene compliance. If an impact on HO infections is seen during the intervention without unintended consequences, then there may be other high risk epidemiologic groups that could benefit from preemptive isolation. If this trial shows a reduction in HO-MDRO rates, this strategy may benefit from a larger-multicenter trial with randomization. This study has the potential to transform how isolation policies are implemented in acute care hospitals and could reduce the risk of pathogen transmission to other HCP and their patients.

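### Aim III's 6-month off/on/off layout puts baseline and withdrawal in almost the same calendar half-year, so an annual cycle can mimic, mask or reverse an intervention effect

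*Protocol*

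**What the plan says.** Aim III describes itself as a "Pre-post withdrawal quasi-experimental study using interrupted time series analysis". On sites: "Six inpatient medical units within Vanderbilt University Hospital will serve as study units". On timing: "After a 6 month baseline period, all units will be transitioned to a 6 month intervention period". Then: "A washout period of 2 weeks will be introduced before a post-intervention withdrawal period of 6 months is implemented". No unit stays off the intervention while the others are on it, and the switches are not staggered.

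Under Analysis, the outcomes are compared across three phases fixed in advance: "6 month baseline period, 6 month intervention period, and 6 month withdrawal period". An interrupted time-series regression with Newey-West standard errors is added, with 12 points per period. The covariates are hand hygiene compliance, PPE compliance and broad-spectrum antimicrobial days of therapy. The only history cited is one year: the "rate of these 6 units combined was 4.62 per 1,000 patient days for 2014". The Aim III design, analysis and limitations text does not mention season, a control series or a longer baseline.

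**The concern.** The withdrawal phase is there to strengthen causal inference: if the rate falls on intervention and rises again afterwards, a simple time trend is a poor explanation. That argument fails against a 12-month cycle when each phase lasts six months. The two off-phases then sit in the same part of the year and the on-phase in the other part, so a purely seasonal swing also goes away and comes back.

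The outcome counts only specimens taken for clinical decisions, so seasonal shifts in case mix or culturing would enter it directly. An apparent benefit that reverses, an apparent harm, or no visible effect could each be partly seasonal. The protocol hopes to inform isolation policy, so this matters for how any result is read.

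**Working it through.** **Inputs.** From Aim III, Sample size considerations: "the mean patient days per period will be 4,952 patient days/month for a total of 29,710/period" and "The rate of HO-MDROs on the units of interest is 4.6/1000 patient days for an average of 137 evaluable events per period"; a detectable difference of 1.4/1,000, about 42 events, at 80% power. From Study procedures: phases of 6, 6 and 6 months with a 2-week gap before the last. Assumed, because the protocol does not give them: two-sided 5% test, Poisson counts, a 12-month sinusoid, and its amplitude and phase.

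**1. The plan's own figure.** Events: 29,710 × 0.0046 = 136.7. Effect: 29,710 × 0.0014 = 41.6 events. SE = √[(4.6 + 3.2)/1,000 ÷ 29,710] = 0.512/1,000. Power = Φ(1.4/0.512 − 1.96) = Φ(0.77) = 78%. The stated 80% is reproduced within about 2 points as a baseline-versus-intervention comparison.

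**2. Calendar overlap.** Two weeks is 2/4.345 = 0.46 month. Withdrawal starts 12.46 months after baseline starts, so it shares 6 − 0.46 = 5.54 of 6 months with the baseline window, or 92%.

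**3. Spurious difference with no intervention effect.** For amplitude A, the means of opposite half-years differ by at most 4A/π = 1.27A. Baseline and withdrawal differ by at most 0.15A. Over all phases of the cycle, intervention-minus-baseline and intervention-minus-withdrawal have the same sign in 96%. That is the effect-then-reversal pattern, in either direction.

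**4. False-positive rate, intervention versus baseline.** At the worst phase the two rates still sum to 9.2/1,000, so SE = √(9.2/1,000 ÷ 29,710) = 0.556/1,000. With δ the spurious difference, the rate is Φ(δ/SE − 1.96) + Φ(−δ/SE − 1.96).

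| Amplitude | Largest δ per 1,000 | Events | Worst phase | Average over phases | Best phase |
|---|---|---|---|---|---|
| 5% | 0.29 | 9 | 8% | 7% | 5% |
| 10% | 0.59 | 17 | 18% | 12% | 5% |
| 20% | 1.17 | 35 | 56% | 31% | 5% |

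Example at 20%: 1.171/0.556 = 2.10, and Φ(0.145) = 56%. An amplitude of 1.4/1.273 = 1.10/1,000, or 24% of 4.6, would reproduce the whole design effect.

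**5. Does the time-series model remove it?** Not by itself. Fitted to a 20% cycle with no intervention effect, a model with level and slope changes shows a spurious level change of up to 1.17/1,000 at the first switch. Newey-West errors change the standard error, not the bias.

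**6. Seasonal terms within the 36 half-month points.** A 12-month sine/cosine pair explains 79% of the variance of the on/off indicator, so the variance inflation is 1/(1 − 0.786) = 4.7. Power for 1.4/1,000 is calculated from the least-squares variance, with Poisson variance at 4.6/1,000 (lower figure) or at 3.9/1,000, midway between 4.6 and 3.2 (upper figure):

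| Model | No seasonal terms | Seasonal, 18 months only | Seasonal, +12 months | Seasonal, +24 months |
|---|---|---|---|---|
| Step plus linear trend | 83–88% | 27–31% | 68–75% | 77–83% |
| Separate level and slope changes (level effect) | 24–28% | 15–17% | 28–32% | 32–37% |

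Example, step plus trend at 4.6/1,000: the SE rises from 0.482 to 1.043, so power goes from Φ(1.4/0.482 − 1.96) = 83% to Φ(1.4/1.043 − 1.96) = 27%.

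**The case against.** **Phase and amplitude are unknown.** A reader might infer that any seasonal cycle would mimic an effect that reverses. The documents do not support that. The bias vanishes when peak and trough fall on the switches, and a pure 6-month cycle cancels. An annual cycle can also look like harm or hide a benefit. The start date cannot be read from the timeline, so worst alignment cannot be asserted. The outcome pools six organism groups whose seasons need not coincide, and at 5% amplitude the problem is small. All of this stands, and it is why a range is given. Even so, the bias exceeds half its maximum in about 67% of phases.

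**Covariates.** Antimicrobial use and hand hygiene are measured and will be in the analysis, so part of a seasonal effect may be absorbed. This stands in part: neither covers case mix or culturing. PPE audits are planned only for patients under the preemptive precautions, so they cannot track season across the off-phases.

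**The analysis plan may add seasonal terms.** It may, and the missing term is not itself the defect. The defect is the fixed layout, which leaves such terms little independent information in 18 months.

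**The remedy's gain depends on the model.** This stands. With separate level and slope changes, power is low before season is considered, and extra history helps only modestly.

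**The protocol is modest in its claims.** It calls the study quasi-experimental and suggests a randomized multicenter trial if a reduction is seen. That tempers the claim but does not tell the reader about season.

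**Conclusion.** The point holds as a structural weakness of the design. The phase lengths, the simultaneous switch and the lack of a control align on/off status closely with calendar half-year whatever the start date, so reversal on withdrawal does not discriminate between an intervention effect and an annual cycle.

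The size is conditional. It rests on an assumed sinusoid and an assumed amplitude of 5% to 20%; the documents contain no seasonal data for this outcome. Within that range the consequence runs from none at a favourable phase to a spurious difference of about 35 of the planned 42 events at the worst phase. The documents do not show that seasonality is present, or that a result would necessarily be false. They show that the planned data could not settle the question.

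**What to change.** Keep the conduct of the study as it is and change the data and the model:

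- Where the electronic surveillance system holds comparable data, extract the same outcome and patient-days for the six units for at least 24 months before baseline. Do not rely on 2014 alone, because the units were chosen partly for high rates.
- Include annual harmonic or calendar-month terms in the time-series model, and make that model, not the raw three-phase comparison, the basis for the conclusion.
- State the form of the intervention effect (step, or level and slope) with its power, since the gain from added history depends on it.
- Add non-study medical units over the same dates as a control series if they prove comparable. They were not selected on the same criteria, and patients move from non-study onto study units, so this needs checking.

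The cost is a retrospective extract and some protocol wording, with no extra patients or visits. Earlier laboratory or coding changes must be checked first. The protocol cites only a 2014 rate, so the availability of a longer history has to be confirmed.

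If neither history nor a control can be obtained, list seasonal confounding among the limitations and do not present reversal on withdrawal as evidence of causation.

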# Specific Aim III: To investigate the impact of preemptive Contact Precautions for residents of long-term care facilities admitted to acute care units, including the impact on the rate of hospital acquisition of MDRO and C. difficile and unintended consequences (e.g. frequency of HCP contacts, patient falls) due to this isolation strategy.

**SIGNIFICANCE:** One factor that may impact the effectiveness of the PPE used to prevent transmission of pathogens like MDROs and *C. difficile* centers upon the initial decision to implement these precautions. Specifically, patient selection for isolation precautions could lead to transmission if persons harboring these pathogens are not considered for placement into isolation. With the increasing prevalence of MDROs and *C. difficile*, specific patient populations at greater risk for infection and/or colonization with these organisms have been identified. One such patient population is residents of long term care facilities (LTCF). LTCFs are important reservoirs of MDROs, including MRSA, extended-spectrum beta lactamase (ESBL) producers, MDR *Acinetobacter*, and *C. difficile*. A prospective cohort study evaluating transmission dynamics of MDR gram-negative bacteria (MDRGNB) among LTCF residents during one year of follow up found that 39% of residents acquired at least 1 MDRGNB. A subsequent study evaluating 360 LTCF residents with advanced dementia demonstrated high rates of MDRO colonization at baseline (any MDRO = 45.6%, MDRGNB = 36.9%, MRSA = 12.8%). The proportion of all residents colonized at some point over a 12 month period was even higher: any MDRO, 66.9%; MDRGNB, 54.4%; and MRSA, 27.1%.

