approaches to the identification of patients who may require Contact Precautions. As part of its Guidance for Control of CRE, the CDC noted that "extensive inter-facility sharing of patients across the continuum of care has the potential to facilitate widespread regional transmission of CRE." The guidelines then suggest as a supplementary practice to standard infection control practices the placement into preemptive Contact Precautions patients transferring from high-risk settings, which may include LTCFs. Data are lacking to evaluate if this is a reasonable strategy. A review in *Clinical Microbiologic Review* stated, "[u]pon admission of patients at increased risk of CRE carriage (such as residency in an LTCF . . . ), preemptive isolation while awaiting surveillance culture results can prevent early transmission events." Preemptive Contact Precautions have been suggested for certain high risk groups in extenuating circumstances for other pathogens such as MERS-CoV  with the understanding that targeting high risk populations could mitigate pathogen transmission.

Such an empiric isolation strategy, however, may have unintended consequences. Previous studies have demonstrated that patients placed into Contact Precautions may have more adverse events, depression and delirium, and potentially worse patient satisfaction and quality of care. A prospective cohort study in four acute care facilities performing active surveillance for MRSA demonstrated that Contact Precautions were associated with activities likely to reduce transmission of MDROs such as fewer visits and better hand hygiene at exit, while simultaneously exposing patients to less HCP contact, less visitor contact and other unintended outcomes. In contrast, a recent trial of universal gown and glove use in ICU settings assessed adverse event rates in these units and found patients were no more likely to experience adverse events than in control ICUs.

For study Aim III, we will investigate the impact of preemptive Contact Precautions for residents of LTCFs admitted to acute care units on the rate of hospital acquisition of MDROs and *C. difficile*. We will also examine the potential for unintended consequences (e.g. frequency of HCP contacts, patient falls) due to this isolation strategy.

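### Aim III is framed as acquisition and infection but counts positive clinician-ordered specimens, and nothing in the plan measures how much testing is done.

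*Protocol*

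**What the plan says.** The title of Specific Aim III sets the target as hospital acquisition: "including the impact on the rate of hospital acquisition of MDRO and C. difficile". Under Research Design and Methods, the primary outcome is labelled infections: "Aggregate rates of all hospital-onset (HO)-MDRO infections (Table 3".

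The same paragraph then fixes what is counted. "As active surveillance for these pathogens is not performed at VUH, only culture specimens obtained for clinical decision making will be included". No body site is ruled out. A result is hospital-onset if the specimen was collected more than 3 days after admission. Table 3 defines events by organism and resistance, with no clinical criterion for infection. Events come from VIPER, a platform that follows laboratory results in real time.

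The rate is per patient-day (Sample size considerations). Under Covariates the protocol says "Several factors may affect the impact of the intervention on the primary outcome. These will be measured and included in the analysis" and lists three: hand hygiene compliance, PPE compliance and broad-spectrum antimicrobial days of therapy. The secondary outcomes include HCP contact and vital signs per patient-day, as measures of contact. The number of cultures or tests sent appears nowhere, and the Limitations paragraph does not mention it.

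Study procedures moves all units from baseline to intervention together and then, after a washout, to withdrawal. The Analysis paragraph compares the three phases and adds an interrupted time series with 12 points per period.

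**The concern.** A count of positive clinical specimens per patient-day is the product of two things: how often the organism is present, and how often someone sends a specimen that could find it. A silent acquisition that nobody cultures is never counted. A colonised urine or wound specimen is counted as an infection. So the measured quantity is neither acquisition nor infection, and it moves with testing practice as well as with transmission.

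That would matter less if testing were measured, or if concurrent control units shared the same practice. Neither is so. If fewer specimens were sent on the units during the intervention phase, the rate would fall with no transmission prevented. If more were sent, a real effect would be masked. The Innovation section treats a decrease in hospital-onset infections, without more non-infectious complications, as grounds for a new isolation strategy, so the distinction bears on the conclusion.

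**Working it through.** **Inputs from the protocol.** Baseline rate 4.62 per 1,000 patient-days and long-term care share 4.3–5.6% of admissions (Study sites). Patient-days 29,710 per period, detectable difference 1.4 per 1,000, power 80% (Sample size considerations).

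**Assumptions.** Two-sided 5% test (the protocol does not state the level). Two Poisson counts with equal patient-days, and z = (b − m)/√(b + m), where b and m are the baseline and intervention counts. The chance of a significant reduction is Φ(z − 1.96) with expected counts put in. Positives are proportional to specimens sent. The percentage changes in culturing are scenarios, because the protocol gives no culture volumes.

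**Step 1: the plan's own figure.** b = 4.62 × 29.710 = 137.3 events. The planned reduction is 1.4 × 29.710 = 41.6 events, so m = 95.7. Then z = 41.6/√233.0 = 2.73 and power = Φ(0.77) = 0.78, close to the stated 80%. That figure is not in dispute.

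**Step 2: no true effect, specimens fall on all six units.**

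| Fall in specimens | m | Events lost | z | Chance of a significant reduction |
|---|---|---|---|---|
| 0% | 137.3 | 0 | 0 | 2.5% |
| 10% | 123.5 | 13.7 | 0.85 | 13% |
| 15% | 116.7 | 20.6 | 1.29 | 25% |
| 20% | 109.8 | 27.5 | 1.75 | 42% |
| 30% | 96.1 | 41.2 | 2.70 | 77% |

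A fall of about 30% would imitate the whole planned effect.

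**Step 3: true reduction of 42 events, specimens rise on all six units.** With no change in testing, power is 79%. With 10% more specimens, m = 95.3 × 1.1 = 104.8, z = 2.09 and power is 55%. With 20% more, m = 114.3, z = 1.45 and power is 30%.

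**Step 4: no true effect, specimens fall only in long-term care residents.** Assume they supply events in proportion to admissions: 137.3 × 0.043 = 5.9 to 137.3 × 0.056 = 7.7 events.

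- A 20% fall removes 1.2 to 1.5 events. z is 0.07 to 0.09, and the chance of a significant reduction is 2.9% to 3.1%.
- At a 10% share, to allow for the protocol's remark that its figure is probably too low, a 20% fall gives 3.6%.
- If every culture in these patients stopped, the chance would be 5.5% to 6.8%.

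**Step 5: would a direction-only check on positives per specimen help?** Take b = 137. Significance needs (137 − m)/√(137 + m) ≥ 1.96, that is m ≤ 106, a ratio of 0.78. If specimens fell by 20%, positives per specimen would then stand at 0.78/0.80 = 0.97 of baseline, still pointing downward. With a smaller fall the ratio is lower still. Simulating the 5–20% scenarios agrees: in essentially every run with a significant patient-day reduction, the per-specimen rate also pointed downward. Agreement in direction therefore screens out practically none of these false positives.

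**The case against.** The strongest case against runs as follows.

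- **The definition is disclosed.** The protocol says openly that there is no active surveillance and that only clinical specimens count. This stands. The fault is a label that claims more than the measurement, plus a missing measure of testing. Nothing is concealed.
- **The design has protections.** The withdrawal phase and the time series deal with a steady drift in culturing, which would not reverse when the policy ends. This stands too. They do not deal with a change that begins and ends with the policy.
- **The only mechanism in the text is narrow.** A reader might infer from the Significance section, which reports Contact Precautions "while simultaneously exposing patients to less HCP contact, less visitor contact and other unintended outcomes", that isolation will depress culturing enough to create a false result. The documents do not support that. The mechanism reaches only isolated patients, Step 4 shows how little that moves the aggregate, and the planned contact and vital-sign measures are a partial check on it. The protocol does not link contact to culturing.
- **A testing adjustment may belong in the analysis plan.** That is fair for the model. The outcome label, the covariate list and the data capture are fixed in the protocol, and specimen counts are best specified together with the outcome.
- **Specimen counts are not neutral.** Cultures are sent because infection is suspected, so their number is partly a consequence of the outcome. If the specimens dropped are low-yield ones, positives per specimen rise with no change in infection. This stands, and it is why the adjusted analysis should be a sensitivity analysis and not a replacement.

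**Conclusion.** The point holds as a modest, inexpensive improvement. The aim and the outcome label claim acquisition and infection, the count is of positive clinician-ordered specimens, and the plan cannot separate a change in infection from a unit-wide change in testing that tracks the policy.

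The size depends on an unknown. If culturing fell 10–20% across all six units during the intervention phase only, a false significant reduction would appear about 13–42% of the time in a two-period comparison. If a 20% fall were confined to long-term care residents, the figure would be about 3%. Both rest on positives being proportional to specimens, and the second also on events being proportional to admissions.

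A reader might take 13–42% as the trial's actual false-positive rate. It is not: nothing in the documents shows that culturing will change between phases, and the figures describe a simple comparison of two periods, not the time series.

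**What to change.** 1. From the laboratory feed behind VIPER, count clinical cultures and *C. difficile* tests collected on or after day 4 on the study units in each half-month, matching the time-series points. Report them per 1,000 patient-days by phase.
2. Prespecify a sensitivity analysis of the primary outcome that accounts for testing volume, either as a covariate or as positives per specimen. Judge it by its estimate and confidence interval, not by whether it points the same way as the patient-day rate (Step 5). State that it may be conservative, because specimens are partly a consequence of infection.
3. Call the outcome, and the conclusion drawn from it, hospital-onset positive clinical specimens, in place of acquisition or infection.

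The cost is one data pull, one extra model and a narrower claim. Patient care, study phases and sample size are unchanged. If testing proves stable, the result is easier to defend.
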